5.2.5.3 Other Allowed Dose Interruption for Pembrolizumab

Pembrolizumab may be interrupted for situations other than treatment emergent related AEs such as medical / surgical events or logistical reasons not related to study therapy. Subjects should be placed back on study therapy within 3 weeks of the scheduled interruption, unless otherwise discussed with the sponsor's medical monitor. The reason for dose interruption should be documented in the subject's study record.

5.2.5.4 *Dose Modification for Tabelecleucel*

If ≥ 2 of the initial 6, or ≥ 4 of the initial 12 Cohort 1 subjects experience a DLT in the first 21 days, the dose of tabelecleucel will be reduced to 1×10^6 cells/kg/dose, and the subsequent 12 subjects will be treated with the combination of tabelecleucel at 1×10^6 cells/kg/dose and pembrolizumab at the recommended dose level. Otherwise, all 12 subjects in Cohort 1 will receive tabelecleucel at 2×10^6 cells/kg/dose and pembrolizumab at the recommended dose level. An SDRC composed of representatives from the sponsor and the principal investigators or designated sub-investigators from all sites enrolling subjects in Cohort 1 will review reported DLTs and cumulative safety data to determine further enrollment. The data review will occur as soon as possible after Cycle 1 Day 21 of the last subject in Cohort 1. For additional details on dose stopping rules (refer to Section 3.3 for additional details).

5.2.5.5 *Discontinuation of One Investigational Product*

Upon approval by the medical monitor, a subject may continue to receive 1 investigational product if the other is withheld or discontinued for any reason other than due to a DLT observed during the first 21 days of combination treatment.

5.3 Prior and Concomitant Medications/Therapies

5.3.1 *Permitted Medications/Therapies*

All treatments that the investigator considers necessary for a subject's welfare may be administered at the discretion of the investigator in keeping with the community standards of medical care; however, refer to prohibited medications and therapies in Section 5.3.1.1. All concomitant medication will be recorded, including all prescription, over-the-counter, herbal supplements, and IV medications and fluids. If changes occur during the study period, documentation of drug dosage, frequency, route, and date should also be recorded.

The investigator or qualified designee will review prior medication use, including any protocol-specified washout requirement, and record prior medication taken by the subject within 30 days before the first dose of investigational product and 30 days after the last dose of investigational product should be recorded. Concomitant medications administered after 30 days after the last dose of investigational product should be recorded if related to any serious AEs (SAEs) and AEs of special interest as defined in Section 8.2.

5.3.1.1 *Rescue Medications and Supportive Care*

Subjects should receive appropriate supportive care measures as deemed necessary by the investigator. Suggested supportive care measures for the management of AEs with potential immunologic etiology are outlined along with the dose modification guidelines in Section 5.2.5 (Table 5). Where appropriate, these guidelines include the use of oral or intravenous treatment with corticosteroids, as well as additional anti-inflammatory agents if symptoms do not improve with administration of corticosteroids. Note that several courses of steroid tapering may be necessary as symptoms may worsen when the steroid dose is decreased. For each disorder, attempts should be made to rule out other causes such as metastatic disease or bacterial or viral

infection, which might require additional supportive care. The treatment guidelines are intended to be applied when the investigator determines the events to be related to pembrolizumab.

If a pembrolizumab-related toxicity requires > 0.5 mg/kg of prednisone equivalent, then tabelecleucel should be held until the steroids are tapered to below 0.5 mg/kg.

Note: If after the evaluation the event is determined not to be related to pembrolizumab, the investigator does not need to follow the treatment guidance (as outlined below). Refer to [Table 5](#) in Section [5.2.5](#) for guidelines regarding dose modification and supportive care.

It may be necessary to perform conditional procedures such as bronchoscopy, endoscopy, or skin photography as part of evaluation of the event.

5.3.2 Prohibited Medications/Therapies

Medications or vaccinations specifically prohibited in the exclusion criteria (Section [4.2.2](#)) are not allowed during the ongoing study. If there is a clinical indication for any medication or vaccination specifically prohibited during the study, discontinuation from study therapy or vaccination may be required. The investigator should discuss any questions regarding this with the sponsor's medical monitor. The final decision on any supportive therapy or vaccination rests with the investigator and/or the subject's primary physician. However, the decision to continue the subject on study therapy requires the mutual agreement of the investigator, the sponsor, and the subject.

Listed below are specific restrictions for concomitant therapy or vaccination during the course of the study:

- Antineoplastic systemic chemotherapy or biological therapy
- Immunotherapy not specified in this protocol
- Chemotherapy not specified in this protocol
- Investigational products other than pembrolizumab or tabelecleucel
- Radiation therapy
 - Note: Radiation therapy to a symptomatic solitary lesion or to the brain may be allowed at the investigator's discretion
- Live vaccines within 30 days prior to the first dose of investigational product and while participating in the study. Examples of live vaccines include, but are not limited to, the following: measles, mumps, rubella, varicella/zoster, yellow fever, rabies, bacille Calmette-Guerin, and typhoid vaccine. Seasonal influenza vaccines for injection are generally killed virus vaccines and are allowed. However, intranasal influenza vaccines (eg, Flu-Mist[®]) are live attenuated vaccines and are not allowed.
- Systemic glucocorticoids for any purpose other than to modulate symptoms from an AE that is suspected to have an immunologic etiology. The use of physiologic doses of corticosteroids may be approved after consultation with the sponsor's medical monitor.

- Note: Inhaled steroids are allowed for management of asthma.

Subjects who, in the assessment of the investigator, require the use of any of the aforementioned treatments for clinical management should be removed from the study. All treatments that the investigator considers necessary for a subject's welfare may be administered at the discretion of the investigator in keeping with the community standards of medical care.

There are no prohibited therapies during Quarterly Follow-up Phase.

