4.6 Subject Withdrawal Criteria

A subject may withdraw either from (1) investigational product treatment only, in which case the subject will continue protocol defined follow-up assessments or (2) study participation, in which case investigational product and study assessments will be discontinued. Whenever possible, continue protocol-defined follow-up after the subject has discontinued investigational product treatment (refer to Section [6.7](#)).

Investigational product treatment may be discontinued for any of the following reasons:

- Occurrence of an AE that precludes further treatment, refer to Section [5.2.5](#)
- Achieves a sustained CR, refer to Section [5.2.4](#)
- Receives a prohibited treatment, such as use of a different investigational product or non-protocol anti-NPC therapy
- Decision (by subject or investigator) that continued investigational product treatment is not in the subject's best interest

Study participation may be discontinued for any of the following reasons:

- Withdrawal of consent by subject or subject's legally authorized representative
- Early closure of the study by the sponsor
- Subject is lost to follow-up

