6.7 Early Withdrawal

For subjects who discontinue early from treatment, consolidation, or maintenance, the reason for discontinuation should be provided and the End-of-Treatment visit should be performed. The subject will be entered into Quarterly Follow-up, unless consent is withdrawn, for 12 months after the last dose of investigational product (tabelecleucel and/or pembrolizumab).

For a subject who discontinues early from quarterly follow-up, the reason for discontinuation should be provided and the last Quarterly Follow-up Visit will be considered the end-of-study for the subject.

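### Protocol Section 5.3.2 removes subjects who need a prohibited treatment from the study, while Sections 4.6 and 6.7 stop product only and keep follow-up, so survival and safety data can be lost

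*Protocol*

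**What the plan says.** Section 5.3.2 of the protocol lists the therapies not allowed during the study: systemic anticancer therapy and immunotherapy outside the protocol, other investigational products, radiation (with an exception), live vaccines, and systemic glucocorticoids other than for suspected immune-related events. It then says that subjects who, in the investigator's judgement, "require the use of any of the aforementioned treatments for clinical management should be removed from the study". The opening paragraph of the same section is milder: if a prohibited medication is clinically indicated, "discontinuation from study therapy or vaccination may be required". The section closes with a limit of scope: "There are no prohibited therapies during Quarterly Follow-up Phase".

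Section 4.6 separates two kinds of withdrawal. One is from "investigational product treatment only, in which case the subject will continue protocol defined follow-up assessments". The other is from "study participation, in which case investigational product and study assessments will be discontinued". Among the reasons for the first kind it lists: "Receives a prohibited treatment, such as use of a different investigational product or non-protocol anti-NPC therapy". For the second kind it lists only withdrawal of consent, early closure by the sponsor and loss to follow-up. Whenever possible, sites are to "continue protocol-defined follow-up after the subject has discontinued investigational product treatment".

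Section 6.7 covers subjects who stop treatment, consolidation or maintenance early. They have the End-of-Treatment visit, and then: "The subject will be entered into Quarterly Follow-up, unless consent is withdrawn, for 12 months after the last dose of investigational product".

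**The concern.** For one event, the need for a prohibited treatment, one section takes the subject off the study while two others stop product at most and keep the subject under observation. Section 4.6 defines leaving the study as the end of study assessments, so the choice of section decides whether data are collected.

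The need for chemotherapy, non-exempt radiation or a non-immune steroid course often marks progression or toxicity. If such subjects leave observation at that moment, the loss is plausibly related to outcome. OS is a secondary endpoint that protocol Section 9.2 summarises by Kaplan-Meier, and the safety profile is a primary objective. Survival could look longer, and late toxicity rarer, than they were.

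**Working it through.** No figure in either document bears on this point, so there is none to reproduce. The check compares the texts first and then illustrates the mechanism.

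**1. The instructions side by side**

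| Place | Trigger | Product | Study follow-up |
|---|---|---|---|
| 5.3.2, removal sentence | listed treatment required | not stated separately | ends (removed from study) |
| 5.3.2, opening paragraph | prohibited medication indicated | stopping may be required | not addressed |
| 4.6 | prohibited treatment received | may be stopped | continues whenever possible |
| 6.7 | early stop of treatment | already stopped | 12 months unless consent withdrawn |

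Rows 1 and 3 cannot both be followed for a subject who needs and receives next-line therapy. The protocol draws the same line elsewhere: Section 5.2.3 stops both products after a DLT and still asks for follow-up to continue.

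**2. When the removal sentence can apply.** Nothing is prohibited in Quarterly Follow-up, so it applies only on treatment or before that phase begins. The End-of-Treatment visit falls 30 ± 5 days after last dose (Section 6.5).

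**3. What can be lost if it is applied**
- The End-of-Treatment visit (6.5).
- SAEs in the remaining window (8.5.1): up to 30 days after stopping product if new NPC therapy starts, otherwise up to 90 days.
- Related AEs after 30 days (8.5). SAP Section 11.1 counts these as treatment-emergent, so they feed the tables.
- Quarterly disease status and survival status (6.6). SAP Section 3.2 lists and plots survival, and SAP Section 11.1 lists all deaths.

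**4. What is barely affected.** Imaging already stops at a new anticancer treatment (7.1.2.3). The SAP censors disease assessments after other anti-NPC therapy (Section 8) and ignores follow-up-stage assessments for ORR and CBR (Section 8.1.1).

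**5. Illustration of the effect on Kaplan-Meier OS.** Every input is assumed: 40% responders with median OS 36 months, 60% non-responders with median OS 12 months, exponential survival, and a fraction f of surviving non-responders censored at month 3.

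Survival to month 3: S(3) = 0.4 × 2^(−3/36) + 0.6 × 2^(−3/12) = 0.3775 + 0.5045 = 0.8821.

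Alive at month 12: responders 0.4 × 2^(−12/36) = 0.3175; non-responders 0.6 × 2^(−12/12) = 0.3000.

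KM(12) = S(3) × [0.3175 + (1 − f) × 0.3000] / [0.3775 + (1 − f) × 0.5045]

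- f = 0: 61.7% (the true value)
- f = 0.25: 0.8821 × 0.5425 / 0.7560 = 63.3%
- f = 0.50: 0.8821 × 0.4675 / 0.6298 = 65.5%
- f = 1: 0.8821 × 0.3175 / 0.3775 = 74.2%, an upper bound

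**6. A second model, also wholly assumed.** Let the hazard before removal, h0, give 70% survival at t = 12 months. Subjects come to need a prohibited therapy at a constant rate q, set so that 10% to 40% do by month 12 in the absence of death. Their hazard then becomes h1 = k × h0. Censoring at that moment makes Kaplan-Meier estimate exp(−h0·t) = 70%. The true value is exp(−(h0+q)·t) + q·exp(−h1·t)·(1 − exp(−a·t))/a, with a = h0 + q − h1. For 25% and k = 2 this is 0.525 + 0.146 = 0.671, an overstatement of 2.9 points. Over the 10% to 40% range the overstatement is 0 at k = 1, 1.1 to 4.8 points at k = 2, and 2.7 to 11.6 points at k = 4.

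**The case against.** The best defence is that Sections 4.6, 6.5 and 6.7 are more specific and more numerous than one sentence in a medication section, so a careful site would keep the subject. That stands as far as it goes: loss is possible, not certain. It does not remove the conflict, because nothing tells a site which text governs.

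Several stronger readings are tempting, and the documents do not support them:

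- **That follow-up is lost in the subjects doing worst.** A subject who stops for progression and reaches Quarterly Follow-up before next-line therapy is outside the removal sentence. Steroids for suspected immune-related events are allowed, radiation to a symptomatic solitary lesion or the brain may be, and physiologic steroid doses may be approved.
- **That Section 5.3.2 cuts off SAEs to day 90 in everyone.** Once new NPC therapy starts, Section 8.5.1 already limits general SAE reporting to 30 days. Removal adds the loss of events inside that window, later related AEs, and the rest of the 90 days for subjects on other prohibited treatments.
- **That the radiation note and the closing line show Section 5.3.2 contradicting itself.** The first is an exception and the second a limit of scope. The real internal tension is between the removal sentence and the opening paragraph.
- **That the OS bias can be read out to 24 months.** Follow-up ends 12 months after last dose, so a subject who stopped near month 3 would be observed only to about month 15 under either reading.
- **That a biased OS estimate will be reported.** The SAP records termination in Phase 1B with 12 subjects (Section 1) and gives survival by listing and swimmer plot only (Section 3.2).

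**Conclusion.** The protocol contradicts itself on whether a subject who needs a prohibited treatment stays under observation. That conclusion rests on the text alone. The consequence is conditional: it requires a site to apply the removal sentence to a subject who has not yet entered Quarterly Follow-up.

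For the Kaplan-Meier OS in the protocol, the loss would plausibly be informative. With 25% to 50% of surviving non-responders removed, the first illustration overstates 12-month OS by roughly 2 to 4 points. The second shows no bias when the hazard does not change after the need arises. Neither model is calibrated to this trial.

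For the analysis now planned, the exposure is a shortened swimmer lane, an incomplete survival or death listing, or missing safety events. Each matters more than usual because there are only 12 subjects. ORR is essentially unaffected.

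**What to change.** 1. Reconcile Section 5.3.2 with Sections 4.6 and 6.7 so that needing a prohibited treatment does not by itself end study participation. The End-of-Treatment visit, safety reporting and Quarterly Follow-up then continue unless consent is withdrawn.
2. Record the therapy and its start date. The SAP needs that date to censor later disease assessments.
3. Leave the decision on stopping product to the existing text. Its wording also differs between the opening paragraph and the removal sentence of 5.3.2 and Section 4.6, and the sponsor should reconcile it. This point proposes no rule on treatment.
4. Reconcile the limit in Section 6.6, which ends Quarterly Follow-up at progression, with Section 6.7 and the confirmed-progression branches of Section 15.2, which give 12 months. It is a second route to losing survival data, and correcting 5.3.2 alone would leave it open.
5. As enrolment stopped at 12 subjects, check the disposition records for anyone taken off study under Section 5.3.2. Report the number, with the date and reason for each.

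The cost is a wording change and a short records check. The follow-up visits are already in the schedule.

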6 STUDY PROCEDURES

Study assessments and procedures are tabulated in Section [15.2](#).

6.1 Inventory Check

Subjects must undergo a tabelecleucel inventory check to ensure availability of an appropriately matched and restricted tabelecleucel cell product prior to undergoing screening procedures.

Within 5 to 10 days prior to screening, the following *required* assessments/procedures will be collected or performed after consent is signed:

- Written informed consent by the subject or the subject's legally authorized representative
- High resolution HLA typing (HLA-A, -B, -C, -DRB1, -DQB1) of the subject
- Cytomegalovirus (CMV) antibody status (local laboratory)
- Demographics
- Subject weight
- AEs considered at least possibly related to study procedure(s) after first informed consent

NOTE: Subjects with historical high-resolution HLA typing may submit their data for this inventory check as described in Section [4.2](#).

6.2 Screening

Within 28 days prior to study enrollment (Cycle 1 Day 1), the following *required* assessments/procedures will be collected or performed after consent is signed, unless otherwise specified:

- Written informed consent by the subject or the subject's legally authorized representative
- Verification that subject meets all inclusion and exclusion criteria
- Complete medical history
- Physical examination
- Height and weight

- Performance status: ECOG for subjects > 16 years of age or Lansky score for subjects 12 to 16 years of age
- AEs considered at least possibly related to study procedure(s)
- Concomitant medications
- Vital signs (body temperature, blood pressure (BP), heart rate (HR), and respiratory rate)
- **CC1**
[REDACTED]
- Radiographic assessments (MRI or CT with contrast) as described in Section [7.1](#)
- **CC1**
[REDACTED]
- Hematology panel: complete blood count (CBC) with platelet count and differential
- Coagulation panel: prothrombin time (PT), activated partial thromboplastin time (aPTT), and international normalized ratio (INR)
- Full chemistry panel: sodium, potassium, chloride, total carbon dioxide, blood urea nitrogen (BUN), creatinine, glucose (fasting), total calcium, albumin, total protein, serum creatinine, total bilirubin (TBIL), ALT, AST, alkaline phosphatase, and tests of thyroid function (thyroid stimulating hormone [TSH], T3, and T4)
- **Cohort 1, checkpoint inhibitor (PD-1/PD-L1) failed subjects only:**
 - Tumor/active site biopsy or archival sample as described in Section [7.2](#) (central laboratory); hematology and coagulation panels must be performed prior to biopsy
 - Initial evidence of progressive disease with confirmation assessment retrospective analysis at a central vendor, refer to inclusion criterion [4.b.ii](#)
- **Cohort 1, checkpoint inhibitor-naïve subjects, and Cohort 2:** Archival tumor block/tumor sections if available (central laboratory)

Within 72 hours prior to Cycle 1 Day 1, the following procedure will be performed:

- Pregnancy test for women of childbearing potential (serum)

6.3 Treatment/Consolidation Phase (21-day Cycles)

All subjects will receive 2 treatment cycles (21-day), and depending on their response to treatment, subjects may receive additional treatment and/or consolidation cycles (21-day), refer to Section [15.2](#). During treatment and consolidation cycles, subjects will receive tabelecleucel on Day 1, Day 8 (± 2), and Day 15 (± 2) and pembrolizumab on Day 1 and have a response assessment within 7 days after Cycle 2 Day 15 and every treatment/consolidation cycle thereafter.

6.3.1 Treatment/Consolidation: Day 1

- Physical examination including weight
- AEs

- Concomitant medications
- Hematology panel: CBC with platelet count and differential
- Abbreviated chemistry panel: serum creatinine, TBILI, ALT, AST, alkaline phosphatase, glucose (fasting) and tests of thyroid function (TSH, T3, and T4)
- **Cycle 1 and Cycle 2 only:** **CCI**
[REDACTED]
[REDACTED]
[REDACTED]
- **Cycle 2 and subsequent cycles:** **CCI**
[REDACTED]
- Investigational product infusions:
 - Pembrolizumab will be administered prior to tabelecleucel
 - Tabelecleucel will be administered 1 hour (\pm 10 minutes) after completion of the administration of pembrolizumab only if no infusion reactions related to pembrolizumab are observed/reported or in the case of such a reaction, the subject has recovered
- Vital signs (body temperature, BP, HR, and respiratory rates) at the following times:
 - immediately before the pembrolizumab infusion
 - within 10 minutes following the conclusion of the pembrolizumab infusion
 - immediately before the tabelecleucel infusion
 - within 10 minutes following the conclusion of the tabelecleucel infusion
 - 1 hour (\pm 10 minutes) after initiation of the tabelecleucel infusion
 - **Cycle 1 only:** 2 hours (\pm 10 minutes) after initiation of the tabelecleucel infusion
 - If the subject experiences symptoms/signs of an infusion reaction, follow-up may be longer, as clinically indicated.

6.3.2 *Treatment/Consolidation: Day 8 and Day 15*

- Physical examination including weight
- Concomitant medications
- AEs
- **CCI**
[REDACTED]
- **Cohort 1, checkpoint inhibitor (PD-1/PD-L1) failed subjects only, at least 1 day after Cycle 1 Day 8 and prior to Cycle 1 Day 15:** tumor/active site biopsy as described in Section 7.2 (central laboratory); hematology and coagulation panels must be performed prior to biopsy
- **Cohort 1, Day 15 only,** Hematology panel: CBC with platelet count and differential

- **Cohort 1, Day 15 only**, Full chemistry panel: sodium, potassium, chloride, total carbon dioxide, BUN, creatinine, glucose (fasting), total calcium, albumin, total protein, serum creatinine, TBIL, ALT, AST, alkaline phosphatase, and tests of thyroid function (TSH, T3, and T4)
- **Cohort 2, at least 1 day after Cycle 1 Day 8 and prior to Cycle 1 Day 15 optional** tumor/active site biopsy as described in Section 7.2 (central laboratory); hematology and coagulation panels must be performed prior to biopsy
- **Cycle 1 and Cycle 2 Day 15 only:** CCI
[REDACTED]
[REDACTED]
[REDACTED]
- Investigational product infusion: tabelecleucel
- Vital signs (body temperature, BP, HR, and respiratory rates) at the following times:
 - immediately before the infusion
 - within 10 minutes following the conclusion of the infusion
 - 1 hour (\pm 10 minutes) after initiation of the infusion
 - If the subject experiences symptoms/signs of an infusion reaction, follow-up may be longer, as clinically indicated.

6.3.3 **Treatment/Consolidation, Observation: Days 16 to 21**

Between Days 16 to 21 of each cycle, the following *required* assessments/procedures will be performed:

- Concomitant medications
- AEs
- **Cycle 2 and subsequent cycles:** Radiographic assessments (MRI or CT with contrast) as described in Section 7.1

